7.1.5 Visit Requirements

Visit requirements are outlined in Section 6.0 - Trial Flow Chart. Specific procedure-related details are provided above in Section 7.1 - Trial Procedures.

7.1.5.1 Screening

7.1.5.1.1 Screening Period

The screening period begins upon signing consent and includes evaluations as described in Section 6.1. The screening period may last up to 42 days.

7.1.5.2 Treatment Period

The treatment period includes the window phase during which pembrolizumab is administered every 21 (+/- 3) days for 6 cycles. Subjects that are determined to have an objective response or stable disease at the point of response assessment prior to cycle 7 (or cycle 10 if pseudoprogression/delayed response) may continue on study in the continuation phase. During the continuation phase pembrolizumab is administered every 21 (+/- 3) days for up to 12 additional cycles to complete a total of up to 18 cycles.

7.1.5.3 End-of-treatment Visit

Thirty days (+/- 14 d) after the last dose of pembrolizumab, irrespective of cause of cessation, an end-of-treatment visit should be performed. However, if a subject requires additional anti-cancer therapy, the off-study visit may occur earlier.

The off-study visit will include laboratory studies, medical history, physical exam, remission status, concomitant medications, adverse events, and documentation of any ECI and subsequent management, as in Section 6.0. All AEs that occur prior to the end-of-treatment visit should be recorded. Subjects with an AE of Grade > 1 will be followed until the resolution of the AE to Grade 0-1 or until the beginning of a new anti-neoplastic therapy, whichever occurs first. SAEs that occur within 90 days of the end of treatment or before initiation of a new anti-cancer treatment should also be followed and recorded.

After the end-of-study visit, additional follow-up will be conducted as per routine standard of care for up to 5 years unless other criteria for withdrawal are met (see Section 5.6). Long-term follow-up may be performed at patients' local physician's offices. Long-term follow-up will assess survival and disease progression; for clarification, subjects may be contacted by the study team until death, subject withdrawal of consent, lost to follow-up, or study termination, whichever occurs first.

7.2 Assessing and Recording Adverse Events

An adverse event is defined as any untoward medical occurrence in a patient or clinical investigation subject administered a pharmaceutical product and which does not necessarily have to have a causal relationship with this treatment. An adverse event can therefore be any unfavorable and unintended sign (including an abnormal laboratory finding, for example), symptom, or disease temporally associated with the use of a medicinal product or protocol-specified procedure, whether or not considered related to the medicinal product or protocol-specified procedure. Any worsening (i.e., any clinically significant adverse change in frequency and/or intensity) of a preexisting condition that is temporally associated with the use of the Merck's product, is also an adverse event.

Merck product includes any pharmaceutical product, biological product, device, diagnostic agent or protocol-specified procedure, whether investigational (including placebo or active comparator medication) or marketed, manufactured by, licensed by, provided by or distributed by Merck for human use.

Adverse events may occur during the course of the use of Merck product in clinical trials or within the follow-up period specified by the protocol, or prescribed in clinical practice, from overdose (whether accidental or intentional), from abuse and from withdrawal.

Adverse events may also occur in screened subjects during any pre-allocation baseline period as a result of a protocol-specified intervention, including washout or discontinuation of usual therapy, diet, placebo treatment or a procedure.

Progression of the cancer under study is not considered an adverse event unless it is considered to be drug related by the investigator.

Adverse events grade 3 and higher, as well as AEs requiring clinical intervention/dose modification, ECIs and SAEs of any grade, will be recorded from the time the consent form is signed up until 90 days following the last dose of pembrolizumab and at each examination on the Adverse Event case report forms/worksheets. The reporting timeframe for adverse events meeting any serious criteria is described in section 7.2.3.1.

7.2.1 Definition of an Overdose for This Protocol and Reporting of Overdose to Merck

For purposes of this trial, an overdose of pembrolizumab will be defined as any dose of 1,000 mg or greater (≥ 5 times the indicated dose). No specific information is available on the treatment of overdose of pembrolizumab. Appropriate supportive treatment should be provided if clinically indicated. In the event of overdose, the subject should be observed closely for signs of toxicity. Appropriate supportive treatment should be provided if clinically indicated.

If an adverse event(s) is associated with (“results from”) the overdose of a Merck product, the adverse event(s) is reported as a serious adverse event, even if no other seriousness criteria are met.

If a dose of Merck’s product meeting the protocol definition of overdose is taken without any associated clinical symptoms or abnormal laboratory results, the overdose is reported as a non-serious Event of Clinical Interest (ECI), using the terminology “accidental or intentional overdose without adverse effect.”

All reports of overdose with and without an adverse event must be reported within 2 working days of investigator knowledge to Merck Global Safety. (Attn: Worldwide Product Safety; [contact])

7.2.2 Reporting of Pregnancy and Lactation to the Sponsor and to Merck

Although pregnancy and lactation are not considered adverse events, it is the responsibility of investigators or their designees to report any pregnancy or lactation in a subject (spontaneously reported to them), including the pregnancy of a male subject's female partner that occurs during the trial or within 120 days of completing the trial completing the trial, or 30 days following cessation of treatment if the subject initiates new anticancer therapy, whichever is earlier. All subjects and female partners of male subjects who become pregnant must be followed to the completion/termination of the pregnancy. Pregnancy outcomes of spontaneous abortion, missed abortion, benign hydatidiform mole, blighted ovum, fetal death, intrauterine death, miscarriage and stillbirth must be reported as serious events (Important Medical Events). If the pregnancy continues to term, the outcome (health of infant) must also be reported.

Such events must be reported within 2 working days of investigator knowledge to Merck Global Safety. (Attn: Worldwide Product Safety; [contact])

7.2.3 Reporting of Adverse Events/Adverse Reactions

7.2.3.1 Serious Adverse Events

A serious adverse event is any adverse event occurring at any dose or during any use of Merck’s product that:

- Results in death;
- Is life threatening;
- Results in persistent or significant disability/incapacity;
- Results in or prolongs an existing inpatient hospitalization;
- Is a congenital anomaly/birth defect;
- Is a new cancer (that is not a condition of the study);
- Is associated with an overdose;
- Is an other important medical event

Refer to Table 6 for additional details regarding each of the above criteria.

Any serious adverse event, or follow up to a serious adverse event, including death due to any cause other than progression of the cancer under study that occurs to any subject from the time the consent is signed through 90 days following cessation of treatment, or the initiation of new anti-cancer therapy, whichever is earlier, whether or not related to Merck product, must be reported within 2 business days of investigator knowledge to Merck Global Safety.

Non-serious Events of Clinical Interest will be forwarded to Merck Global Safety and will be handled in the same manner as SAEs.

Additionally, any serious adverse event, considered by an investigator who is a qualified physician to be related to Merck product that is brought to the attention of the investigator at any time outside of the time period specified in the previous paragraph also must be reported immediately to Merck.

SAE reports and any other relevant safety information are to be forwarded to the Merck Global Safety [contact]

A copy of all 15 Day Reports and Annual Progress Reports is submitted as required by FDA, Pharmaceutical and Medical Devices agency (PMDA) or other local regulators. Investigators will cross reference this submission according to local regulations to the Merck Investigational Compound Number (IND, CSA, etc.) at the time of submission. Additionally, investigators will submit a copy of these reports to Merck & Co., Inc. (Attn: Worldwide Product Safety; [contact]) at the time of submission to FDA.

All subjects with serious adverse events must be followed up for outcome.

7.2.3.2 Events of Clinical Interest

Selected non-serious and serious adverse events are also known as Events of Clinical Interest (ECI). See appendix 11.10, ECI Guidance Document, for management and reporting of ECI. ECI and must be recorded as such on the Adverse Event case report forms/worksheets and reported within 2 business days of investigator knowledge to Merck Global Safety. (Attn: Worldwide Product Safety; [contact]) Events of clinical interest for this trial include:

1. An overdose of Merck product, as defined in Section 7.2.1 - Definition of an Overdose for This Protocol and Reporting of Overdose to Merck, that is not associated with clinical symptoms or abnormal laboratory results.
2. An elevated AST or ALT lab value that is greater than or equal to 3X the upper limit of normal and an elevated total bilirubin lab value that is greater than or equal to 2X the upper limit of normal and, at the same time, an alkaline phosphatase lab value that is less than 2X the upper limit of normal, as determined by way of protocol-specified laboratory testing or unscheduled laboratory testing. *

***Note:** These criteria are based upon available regulatory guidance documents. The purpose of the criteria is to specify a threshold of abnormal hepatic tests that may require an additional evaluation for an underlying etiology. The trial site guidance for assessment and follow up of these criteria can be found in the Investigator Trial File Binder (or equivalent).

1. Additional adverse events:

A separate guidance document has been provided entitled “Event of Clinical Interest Guidance Document” (previously entitled, “Event of Clinical Interest and Immune-Related Adverse Event Guidance Document”). This document can be found in Appendix 4 and provides guidance regarding identification, evaluation and management of ECIs and irAEs.

ECIs (both non-serious and serious adverse events) identified in this guidance document from the date of first dose through 90 days following cessation of treatment, or 30 days after the initiation of a new anticancer therapy, whichever is earlier, need to be reported within 2 business days to Merck Global Safety. (Attn: Worldwide Product Safety; [contact]), regardless of attribution to study treatment, consistent with standard SAE reporting guidelines.

Subjects should be assessed for possible ECIs prior to each dose. Lab results should be evaluated and subjects should be asked for signs and symptoms suggestive of an immune-related event. Subjects who develop an ECI thought to be immune-related should have additional testing to rule out other etiologic causes. If lab results or symptoms indicate a possible immune-related ECI, then additional testing should be performed to rule out other etiologic causes. If no other cause is found, then it is assumed to be immune-related.

7.2.4 Evaluating Adverse Events

An investigator who is a qualified physician will evaluate all adverse events according to the NCI Common Terminology for Adverse Events (CTCAE), version 4.0. Any adverse event which changes CTCAE grade over the course of a given episode will have each change of grade recorded on the adverse event case report forms/worksheets.

All adverse events regardless of CTCAE grade must also be evaluated for seriousness.

Table 6 Evaluating Adverse Events

An investigator who is a qualified physician, will evaluate all adverse events as to:

V4.0 CTCAE Grading	Grade 1	Mild; asymptomatic or mild symptoms; clinical or diagnostic observations only; intervention not indicated.
	Grade 2	Moderate; minimal, local or noninvasive intervention indicated; limiting age-appropriate instrumental ADL.
	Grade 3	Severe or medically significant but not immediately life-threatening; hospitalization or prolongation or hospitalization indicated; disabling; limiting self-care ADL.
	Grade 4	Life threatening consequences; urgent intervention indicated.
	Grade 5	Death related to AE
Seriousness	A serious adverse event is any adverse event occurring at any dose or during any use of Merck product that:	
	†Results in death; or	
	†Is life threatening; or places the subject, in the view of the investigator, at immediate risk of death from the event as it occurred (Note: This does not include an adverse event that, had it occurred in a more severe form, might have caused death.); or	
	†Results in a persistent or significant disability/incapacity (substantial disruption of one's ability to conduct normal life functions); or	
	†Results in or prolongs an existing inpatient hospitalization (hospitalization is defined as an inpatient admission, regardless of length of stay, even if the hospitalization is a precautionary measure for continued observation. (Note: Hospitalization [including hospitalization for an elective procedure] for a preexisting condition which has not worsened does not constitute a serious adverse event.); or	
	†Is a congenital anomaly/birth defect (in offspring of subject taking the product regardless of time to diagnosis); or	
	Is a new cancer; (that is not a condition of the study) or	
	Is an overdose (whether accidental or intentional). Any adverse event associated with an overdose is considered a serious adverse event. An overdose that is not associated with an adverse event is considered a non-serious event of clinical interest and must be reported within 24 hours.	
	Other important medical events that may not result in death, not be life threatening, or not require hospitalization may be considered a serious adverse event when, based upon appropriate medical judgment, the event may jeopardize the subject and may require medical or surgical intervention to prevent one of the outcomes listed previously (designated above by a †).	
Duration	Record the start and stop dates of the adverse event. If less than 1 day, indicate the appropriate length of time and units	
Action taken	Did the adverse event cause the Merck product to be discontinued?	
Relationship to test drug	Did the Merck product cause the adverse event? The determination of the likelihood that the Merck product caused the adverse event will be provided by an investigator who is a qualified physician. The investigator's signed/dated initials on the source document or worksheet that supports the causality noted on the AE form, ensures that a medically qualified assessment of causality was done. This initialed document must be retained for the required regulatory time frame. The criteria below are intended as reference guidelines to assist the investigator in assessing the likelihood of a relationship between the test drug and the adverse event based upon the available information.	
	The following components are to be used to assess the relationship between the Merck product and the AE; the greater the correlation with the components and their respective elements (in number and/or intensity), the more likely the Merck product caused the adverse event (AE):	
	Exposure	Is there evidence that the subject was actually exposed to the Merck product such as: reliable history, acceptable compliance assessment (pill count, diary, etc.), expected pharmacologic effect, or measurement of drug/metabolite in bodily specimen?
	Time Course	Did the AE follow in a reasonable temporal sequence from administration of the Merck product? Is the time of onset of the AE compatible with a drug-induced effect (applies to trials with investigational medicinal product)?
	Likely Cause	Is the AE not reasonably explained by another etiology such as underlying disease, other drug(s)/vaccine(s), or other host or environmental factors

Relationship to Merck product (continued)	The following components are to be used to assess the relationship between the test drug and the AE: (continued)	
	Dechallenge	
Was the Merck product discontinued or dose/exposure/frequency reduced? If yes, did the AE resolve or improve? If yes, this is a positive dechallenge. If no, this is a negative dechallenge.
 
(Note: This criterion is not applicable if: (1) the AE resulted in death or permanent disability; (2) the AE resolved/improved despite continuation of the Merck product; or (3) the trial is a single-dose drug trial); or (4) Merck product(s) is/are only used one time.)

	Rechallenge	
Was the subject re-exposed to the Merck product in this study? If yes, did the AE recur or worsen? If yes, this is a positive rechallenge. If no, this is a negative rechallenge.
 
(Note: This criterion is not applicable if: (1) the initial AE resulted in death or permanent disability, or (2) the trial is a single-dose drug trial); or (3) Merck product(s) is/are used only one time).
 
NOTE: IF A RECHALLENGE IS PLANNED FOR AN ADVERSE EVENT WHICH WAS SERIOUS AND WHICH MAY HAVE BEEN CAUSED BY THE MERCK PRODUCT, OR IF REEXPOSURE TO THE MERCK PRODUCT POSES ADDITIONAL POTENTIAL SIGNIFICANT RISK TO THE SUBJECT, THEN THE RECHALLENGE MUST BE APPROVED IN ADVANCE BY THE U.S. CLINICAL MONITOR AS PER DOSE MODIFICATION GUIDELINES IN THE PROTOCOL.

	Consistency with Trial Treatment Profile	Is the clinical/pathological presentation of the AE consistent with previous knowledge regarding the Merck product or drug class pharmacology or toxicology?
The assessment of relationship will be reported on the case report forms /worksheets by an investigator who is a qualified physician according to his/her best clinical judgment, including consideration of the above elements.		
Record one of the following		Use the following scale of criteria as guidance (not all criteria must be present to be indicative of a Merck product relationship).
Yes, there is a reasonable possibility of Merck product relationship.	There is evidence of exposure to the Merck product. The temporal sequence of the AE onset relative to the administration of the Merck product is reasonable. The AE is more likely explained by the Merck product than by another cause.	
No, there is not a reasonable possibility Merck product relationship	Subject did not receive the Merck product OR temporal sequence of the AE onset relative to administration of the Merck product is not reasonable OR there is another obvious cause of the AE. (Also entered for a subject with overdose without an associated AE.)	

7.2.5 Sponsor-Investigator Responsibility for Reporting Adverse Events

The sponsor-investigator is required to report all problems, events and information that require prompt reporting to the IRB within ten (10) calendar days of learning of the problem. The sponsor-investigator will also report serious, unexpected, suspected adverse reactions and other significant safety information to FDA as required under 21 CFR 312.32.

Adverse events grade 3 and higher, as well as AEs requiring clinical intervention/dose modification, ECIs, and SAEs of any grade, will be reported from the time of signing of consent up until 90 days following the last dose of pembrolizumab.

If a problem, event or information is determined to be an unanticipated problem involving risks to participants or others, it will be reviewed by the convened IRB, appropriate steps will be taken and it will be reported to appropriate institutional and governmental officials as provided under applicable law.

For the purposes of this protocol, the terms Adverse Event, Serious Adverse Event (Related, Possibly Related or Unexpected) and Unanticipated Problem are defined in accordance with the most current Fred Hutchinson Cancer Research Center Institutional Review Board Policy 2.6.

Routine Reporting

Routine reporting is required for all grade 3, 4 and 5 adverse events. Routine reporting will be conducted in accordance with applicable FDA regulations, and agreements with Merck.

Expedited Reporting

With respect to each research study he or she is conducting, the principal investigator must ensure that the following problems, events, and information involving risks to research participants or others are reported to the IRB not later than ten (10) calendar days after he or she first becomes aware of the problem, event, or information.

Adverse Events Requiring Expedited Reporting

Adverse events require expedited reporting if they meet all three of the following criteria:

- (1) unexpected, and
- (2) related or possibly related to the research and
- (3) serious or suggest that the research places research participants or others at a greater risk of physical or psychological harm than was previously known or recognized.

Unless otherwise specified in the Protocol, therapeutic oncology protocols are not required to specify monitoring parameters for Grade I or II toxicities as described in the Common Terminology Criteria for Adverse Events published by the National Cancer Institute. These adverse events are expected and occur routinely in the subject population being studied. They should be monitored and treated in the practice of routine clinical care.

8.0 STATISTICAL ANALYSIS PLAN

8.1 Statistical Analysis Plan Summary

This is a single-arm phase II study designed to show a statistically significantly improved overall response rate (ORR) from the fixed benchmark of 25%. This rate is based on early data of efficacy of immune checkpoint modulating antibodies used in treating FL in the relapsed and refractory setting (4). Though representing a lower ORR than has been shown for other first-line therapeutic strategies in iBCL (19) this threshold was chosen with consideration for pembrolizumab's novel mechanism of action compared with standard iBCL treatments and the potential for achieving long-term remissions with low toxicity (20).

8.2 Statistical Analysis Plan

We shall use the backbone of a Simon two-stage minimax design for this trial with an additional look to potentially stop for futility based on outcomes observed in two specific histology subgroups (follicular lymphoma, marginal-zone lymphoma). With 33 patients, a Simon two-stage minimax design yields 90% to observe an ORR that is statistically significantly higher (at the one-sided significance level of .05) than the fixed ORR rate of 25% if the assumed-true ORR with the regimen currently proposed is 50%. In the first stage, if we observe 4 or fewer responses among 16 patients (25% or less), consideration will be given to terminating the study due to lack of sufficient efficacy. On the other hand, if 5 or more responses are seen among the first 16 patients (and observed ORR of at least 31%), an additional 17 patients will be enrolled. At this point, if 13 or more responses are seen among the 33 patients (an observed rate of at least 39%), the study will conclude that the proposed treatment is potentially efficacious and worthy of further study.

The modification to the above Simon two-stage design will include an interim look within the first stage, with this interim look consisting of subtype-specific analyses. If there are 0 responses among the first 6 patients with follicular lymphoma, accrual of such patients will be stopped. The same rule will be applied to patients with marginal-zone lymphoma. If the true probability of response is 50%, the probability of seeing 0 responses among 6 patients is .016. This additional look has a small impact on the power of the Simon design (since, under the alternative hypothesis, we may incorrectly stop at least one group for futility, hence decreasing the power (i.e., increasing the Type II error or false negative rate). In particular, if one assumes a 50% ORR (consistent with the alternative hypothesis in the Simon design) in both subtypes with an equal probability of enrollment to each subtype, the addition of the subtype-specific rules from above decreases the power from 90% to approximately 87% (estimated from 5,000 simulations). Note that if in each subtype there are 0 responses in the first 6 patients, for a total of 0/12, these results would lead to stopping the trial per the Simon two-stage rules as it would not be possible to achieve at least 5 responses in the first 16 patients.

If the study is stopped due to lack of efficacy in a histologic subgroup, the study may only be reopened to accrual for patients with that histology with modifications (e.g. addition of a

second agent, change in dosing, etc) that have been reviewed and approved where appropriate by the sponsor, scientific review, and relevant regulatory bodies.

Suspension rules for toxicity:

Prior studies treating patients that have not received prior chemotherapy suggest that the rates of grade ≥ 3 immune-related AEs occur in approximately 10% of patients (Reck et al, NEJM 2016). Infusion reactions of \geq grade 3 are less common and less consistently reported in publications. For this reason, we will initiate a suspension rule for infusion- or immune-related AEs of \geq grade 3 of up to 12%. This will be deemed to occur if the lower level of a one-sided 80% confidence interval for immune-related or infusional AEs of \geq grade 3 exceeds 12%.

Operationally, the study will be suspended and referred to the DSMC for consideration of results and appropriate modification or termination of the study if

- 3 out of the first 11 or fewer, 5 out of the first 22 or fewer, 6 out of the first 33 or fewer have \geq grade 3 immune related or infusional AEs

If the true probability of \geq grade 3 AEs is 5%, the probability of suspending the trial due to excess AEs after 11, 22, and 33 patients is approximately <0.02, 0.02, and 0.02, respectively. If the true probability of \geq grade 3 AEs is 30%, the probability of suspension due to excess AE is approximately 0.80, 0.94, and 0.99, respectively. (Probabilities of suspension estimated from 5,000 simulations).

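### Sections 2.1 and 8.2 disagree on the histology futility look, the stated 87% power does not describe the design as worded, and a pass after a closure is not limited to the histology left open

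*Combined protocol and SAP*

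**What the plan says.** Section 8.2 starts from a Simon two-stage minimax design: 16 patients, then "an additional 17 patients will be enrolled" if at least 5 of the 16 respond. At 4 or fewer, "consideration will be given to terminating the study due to lack of sufficient efficacy". The final rule is pooled over follicular lymphoma (FL) and marginal zone lymphoma (MZL): "if 13 or more responses are seen among the 33 patients (an observed rate of at least 39%), the study will conclude" in favour of the regimen. The conclusion reads in full: "the study will conclude that the proposed treatment is potentially efficacious and worthy of further study".

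A look by histology is added within the first stage: "If there are 0 responses among the first 6 patients with follicular lymphoma, accrual of such patients will be stopped". The same rule applies to MZL. Section 2.1 describes this look as taking place after 5 subjects in each histology, not 6.

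Patients of a closed histology stay in the pooled count. Section 8.2 notes that no responses in either group, "for a total of 0/12, these results would lead to stopping the trial per the Simon two-stage rules", and section 8.3.1 computes the overall response rate (ORR) over everyone treated. Section 8.2 says the extra look "decreases the power from 90% to approximately 87% (estimated from 5,000 simulations"), assuming 50% ORR in both histologies "with an equal probability of enrollment to each subtype". A later paragraph of 8.2 bars reopening a closed histology without approved changes.

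**The concern.** The look by histology matters most when one histology responds and the other does not. The plan leaves three things unsettled for that case.

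- **Size of the look.** It is 5 in section 2.1 and 6 in section 8.2.
- **Freed places.** The plan does not say whether the open histology fills the trial to 33. The references to 17 additional patients and to 33 patients suggest that it does. The stated loss of power suggests that it does not. If it does not, the plan gives nothing to replace the thresholds of 16, 33 and 13.
- **Scope of a pass.** A pass after a closure is worded for the treatment as a whole. The bar on reopening governs accrual, not what may be concluded. A positive result could then be read as covering a histology that the trial itself closed for lack of efficacy.

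**Working it through.** **Inputs.** From section 8.2: null ORR 25%, alternative 50%, one-sided 0.05, stop at 4 or fewer of 16, pass at 13 or more of 33, closure at 0/6, equal chance of each histology, 5,000 simulations. From section 2.1: a look after 5.

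**1. Base design.** P(pass) is the sum over x = 5 to 16 of P(X1 = x) × P(X2 ≥ 13 − x), with X1 ~ Bin(16, p) and X2 ~ Bin(17, p). This gives 0.0449 at p = 0.25 and 0.9017 at p = 0.50, so the stated 90% reproduces. P(0/6) = 0.5^6 = 0.0156 matches the stated .016; P(0/5) = 0.5^5 = 0.031.

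**2. Power with the look added.** This is an exact enumeration over 33 places, each FL or MZL with probability one half, ORR 50% in both, outcomes known at once, and the 4/16 stop applied. Under no refill, places that fall to a closed histology stay empty and the thresholds 5 and 13 are unchanged.

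| Look | Refilled to 33 | Not refilled | Any closure counted as failure |
|---|---|---|---|
| 0/6 (section 8.2) | 90.2% | 88.7% | 88.6% |
| 0/5 (section 2.1) | 90.2% | 86.7% | 86.4% |

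Refilling costs no power here, because a place moved to the other histology still has a 50% chance of response. A double closure at 0/12 leaves at most 4 responses in 16, which the Simon rule stops anyway.

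**3. Comparison with 87%.** The simulation standard error is √(0.87 × 0.13 / 5,000) = 0.0048. With 5,000 runs, a true 88.7% would print as 87% (86.5% to 87.5%) in about 0.3% of simulation sets. A true 86.7% would do so in about 60%, and a true 90.2% practically never. A shortcut product for the 0/6 rule, 0.9017 × (63/64)² = 0.874, also rounds to 87%, but the plan says that it simulated.

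**4. What a pass rests on after one closure.** With refill, the open histology supplies 33 − 6 = 27 patients and needs 13 of them: 13/27 = 48%, against the stated 13/33 = 39%. The true ORRs below are illustrative assumptions, not figures from the plan. Enrolment is equal, outcomes are immediate and the 0/6 rule is used. Ranges run from a binding to a non-binding 4/16 stop.

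| True ORR, stronger / weaker | Only the weaker closes | Pass given that, refill | Pass given that, no refill |
|---|---|---|---|
| 60% / 10% | 53% | 81% to 93% | 15% to 16% |
| 50% / 0% | 98% | 52% to 66% | about 5% |

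At 60%/10%, a pass with a closed histology therefore occurs in 0.53 × 0.81 = 43% to 0.53 × 0.93 = 49% of all trials with refill, and in about 0.53 × 0.15 = 8% without.

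**The case against.** The strongest reply is that pooling is deliberate. This is a pilot seeking a preliminary estimate, its conclusion claims only potential efficacy, and no power within a histology is promised. Under the plan's own 50%/50% assumption, at least one histology closes in only 1 − (63/64)² = 3% of trials. All of that stands. It does not say what happens once the plan's own closure rule has fired, which is the point here.

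A reader might infer more than the documents support in five places.

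- **That the 87% is shown not to belong to the 0/6 rule.** The plan says approximately; 88.7% is within 2 points; the product shortcut gives 87.4%; and the neighbouring .016 and 0/12 are computed for 6. A 0/5 look without refill is the closest match, but a leftover 0/5 calculation is only an inference.
- **That the soft wording of the 4/16 stop is an error.** If the stop is ignored, P(X ≥ 13 of 33) at 25% is 0.0484, still below 0.05, and the base power rises to 91.9%.
- **That the plan asserts efficacy in a closed histology.** It does not; the conclusion is simply not limited.
- **That ORR by histology would be withheld.** Section 8.3.1 does not exclude it. It only does not plan it, although section 8.3.2.2 measures PFS by disease cohort.
- **That refilling is the right choice.** It is a trade-off for the sponsor, and the 87% points the other way.

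**Conclusion.** The point holds in this form. Sections 2.1 and 8.2 contradict each other on 5 or 6. The 87% does not describe a trial filled to 33, where the 0/6 rule costs nothing (90.2%), and it is about 2 points below the same rule without refill (88.7%). The figure thus implies no refill, while the wording implies refill, and without refill no usable thresholds are given. Separately, a pass after a closure is not limited to the histology left open.

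The refill choice matters little when both histologies respond at 50%, and a great deal when they differ: 81% to 93% against 15% to 16% at 60%/10%, given closure. Those rates rest on assumed ORRs, equal enrolment and immediate outcomes. Response is read after six 3-week cycles, so more patients of the failing histology may enter before it closes. Allowing for a lag of about 7 patients and a hold at patient 16, the 60%/10% refill figures fall to 58% and 83%. The direction of the finding does not change.

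**What to change.** 1. Reconcile sections 2.1 and 8.2 on whether the look is after 5 or 6 patients per histology.
2. State in 8.2 whether the open histology fills the remaining places to 33. If it does not, state which thresholds replace 16, 33 and 13.
3. Rerun the simulation for the final rule and restate the 87%. For 0/6, expect about 90% with refill and about 89% without.
4. Add to 8.2 that, after a closure, any positive conclusion names only the histology left open. Add to 8.3.1 the ORR with a 95% two-sided confidence interval for FL and MZL separately.

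The cost is a few sentences and one simulation, with no extra patients. The downside is a narrower claim after a closure and wide intervals by histology. At the pass mark with refill, 13/27 has an exact 95% interval of 29% to 68% and 0/6 one of 0% to 46%, against 23% to 58% for the pooled 13/33.
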